8.2 Recording and Reporting

The safety reporting period will commence at the point of consent and end at the final study visit. The intervention (ET and signposting) is extremely low risk and therefore unlikely to result in AEs or SAEs. However, as participants are people with social care needs, it is possible that AEs, SAEs, and other safeguarding concerns unrelated to the intervention may arise. The ET workers and the researchers will record the dates and details of any concerns and incidents in a Safeguarding Log. The ET worker or researcher will then notify the CIs, who will review the log and, utilise their experience and judgement to determine if there is a causal relationship between the incident and the study (i.e., if it is an AR or SAR) and if further action is needed. This includes determining if the incident needs to be escalated as an SAR. Actions decided and taken will be recorded in the Log.

If an incident is determined to be an AR or SR, it must be entered into REDCap within 24 hours of the research team first becoming aware of it, even if not all information is available at the time of

reporting. The sponsor will be automatically notified when an SAE is entered. Change in condition and new follow-up information should be entered on the digital PenCTU SAE resolution form as soon as it is available or at least within 24 hours of the information becoming available.

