8. SAFETY MONITORING

8.1 Definitions

Term	Definition			
Adverse Event (AE)	An AE is an unfavourable or unintended disease, sign, or symptom that is temporally associated with the intervention, whether or not it is related to that intervention.			
Adverse Reaction (AR)	An AE that, in the opinion of the CIs, has the potential to be related to the intervention (i.e., its relationship to the intervention cannot be ruled out).			
Serious Adverse Event (SAE)	 A SAE is an untoward response that: results in death is life-threatening requires hospitalisation or prolongation of existing hospitalisation results in persistent or significant disability or incapacity consists of a congenital anomaly or birth defect Other events may be considered SAEs if they jeopardise the participant or require an intervention to prevent one of the above consequences. 			
Serious Adverse Reaction (SAR)	A SAE that, in the opinion of the CI, is believed with reasonable probability to be due to the intervention, based on the information provided.			

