8.3 Responsibilities

ET workers and researchers:

- Record AEs, SAEs, and safeguarding concerns in the Safeguarding Log
- Notify the CIs that a new concern or incident has been added to the Log

CI or their delegate:

- Maintain the Safeguarding Log
- Review concerns or incidents added to the Safeguarding Log
- Ensure concerns or incidents are added to participants' notes on SystemOne as required
- Use experience and judgement to assign causality and determine actions required
- Ensure that all SAEs are recorded and reported to PenCTU and the Sponsor
- Ensure that actions decided on are taken
- Report safety information to the DMEC and TSC

DMEC and TSC:

- Conduct periodic reviews of safety information
- Liaise with one another regarding safety issues

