9.2 Statistical Analysis Plan

WP1:

The workshops for developing the training and supervision manual for workers will be recorded. The data will be analysed using realist-informed thematic approach (see below for further detail) and, along with information from a prior realist review, used to generate the manual.

WP2:

The feasibility RCT will be reported in accordance with the CONSORT 2010 statement extension to pilot and feasibility trials (59). Descriptive statistics will be reported for feasibility outcomes: numbers screened, eligible, and recruited; retention rates; measure completion rates and data quality; intervention delivery and fidelity (including univariate and bivariate analysis to assess the bespoke fidelity checklist developed in WP1); and attrition during follow-up. The data will inform a potential full RCT, with variability in candidate primary and secondary measures calculated and a sample size (power calculation) for the full RCT estimated for each. Moreover, missing data will be investigated in the feasibility RCT to determine why these are missing and what can be done to minimise missingness in the future full RCT. Simple descriptive analyses will identify the extent of missing data for various questions and questionnaires in the dataset, and models will be fitted to see whether the probability of missingness is linked to baseline characteristics. No statistical comparisons between treatment groups will be undertaken on baseline or follow-up data, as the study is not designed to test effectiveness. Adverse events will be summarised descriptively.

For the cost-effectiveness feasibility analysis, descriptive statistics including data completeness will be reported for each source. The potential cost of ET will be calculated based on information Empowered Together (Coordinated Social Care in Prison)/ET IRAS ID: 361615 Version 1: 01/08/2025

collected using the bespoke fidelity tool about time spent on training, supervision, developing care plans and other components of intervention delivery. Staff time will be costed based on unit costs from the Personal Social Services Resource Unit (60). The team will also investigate the suitability of the ASCOT SCT4, EQ-5D-5L, or ReQoL-10 to calculate the incremental cost per QALY, and the ICECAP-A for YFC gained as part of a full economic evaluation. The extent to which each outcome measure aligns with changes in the CANFOR-R and meeting of social care needs will also be evaluated.

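### Sections 8.2 and 8.3 disagree on which serious adverse events must be entered in REDCap, and the AE definition does not fit the control arm

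*Protocol*

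**What the plan says.** Section 8.2 starts with a complete record outside the database: "The ET workers and the researchers will record the dates and details of any concerns and incidents in a Safeguarding Log". The CIs then review the Log and "determine if there is a causal relationship between the incident and the study (i.e., if it is an AR or SAR"). Entry in the trial database comes after that judgement: "If an incident is determined to be an AR or SR, it must be entered into REDCap within 24 hours". The sentence that follows says the sponsor is alerted automatically once an SAE has been entered. The reporting period in 8.2 runs from consent to the final study visit.

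Section 8.3 gives the CI, or a delegate, a wider duty: "Ensure that all SAEs are recorded and reported to PenCTU and the Sponsor". Section 8.4 sends all deaths to PenCTU through the eCRF, but refers back to 8.2 for how to report them. Section 10.1 lists SAE reporting among the uses of REDCap and does not limit it to related events.

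Section 8.1 defines an AE as something "temporally associated with the intervention, whether or not it is related to that intervention". An AR is "An AE that, in the opinion of the CIs, has the potential to be related to the intervention". A SAR is an SAE "believed with reasonable probability to be due to the intervention". Section 9.2 adds: "Adverse events will be summarised descriptively".

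**The concern.** Safety reporting normally records every serious event first and attaches the causality judgement as an attribute. Section 8.2 reverses this: the judgement decides whether the stated entry step applies. A researcher who learns that a control participant has been hospitalised finds no instruction in 8.2 to enter the event, and a duty in 8.3 to see that it is reported. The two cannot both be complete.

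The judgement is also not described as blinded. Section 6.3 sends the CIs an automatic email at each randomisation, and section 6.4 does not list them among the blinded staff (the protocol does not say whether the email shows the arm). If the database held mainly events thought to be related, a descriptive summary taken from it would under-record the control arm and unrelated events. That matters in a population where 8.2 itself expects AEs and SAEs unrelated to the intervention.

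**Working it through.** No sample size, power or event count bears on this point, so the check sets the sections against each other.

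**Step 1. What each section requires**

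| Section | Events covered | Depends on causality? | Entry step | Deadline |
|---|---|---|---|---|
| 8.2, Log | All concerns and incidents | No | Safeguarding Log | None stated |
| 8.2, database | AR or SR | Yes | REDCap | 24 hours |
| 8.3 | All SAEs | No | Report to PenCTU and sponsor, route not given | None stated |
| 8.4 | All deaths | No | eCRF | By reference to 8.2 |
| 10.1 | SAEs | No | REDCap | None stated |

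The 24-hour limit for first entry appears only in the row that depends on causality. The automatic sponsor alert, also in 8.2, fires only when an SAE is entered.

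**Step 2. Apply the sections to types of event**

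- *Related SAE, intervention arm.* 8.2 and 8.3 agree: it is entered within 24 hours and the sponsor is alerted.
- *Unrelated SAE, not a death, intervention arm.* 8.3 requires it to be reported. 8.2 gives no instruction to enter it and no deadline.
- *SAE, not a death, control arm.* The same gap. In addition, an AR must be an AE with a possible relation to the intervention, which controls do not receive, so the trigger would hardly ever be met.
- *SAE between consent and randomisation.* The same gap. Section 6.3 places randomisation after consent, screening and baseline assessment, so this interval exists for every participant and lies inside the reporting period.
- *Death, either arm.* 8.4 requires it in the eCRF. The reference back to 8.2 leaves the deadline unclear when the death is judged unrelated.

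**Step 3. Check the definitions**

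Section 8.2 asks about a causal link with the study, while 8.1 defines AR and SAR by relation to the intervention. A control participant harmed by a research procedure would meet the first test and not the second. The abbreviation SR is defined neither in 8.1 nor in the list of abbreviations. SAR is presumably meant.

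**Step 4. Does the AR/SAR threshold lose events?**

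The bar is lower for an AR (relation cannot be ruled out) than for a SAR (reasonable probability). An SAE that misses the SAR bar but whose relation cannot be ruled out is still an AR, and so still triggers entry. The difference is untidy but does not itself cause loss.

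**The case against.** The strongest reply is that the protocol, read as a whole, plainly intends all SAEs to reach the database and that 8.2 is one badly worded sentence. 8.3 covers all SAEs, 10.1 makes REDCap the SAE tool, the sponsor alert in 8.2 itself refers to an SAE and not a SAR, and 9.3 has weekly scripts checking that SAE forms are complete. This is a fair account of the intention. It does not remove the conflict: 8.2 is the operative instruction and has the only first-entry deadline, and the scripts in 9.3 are not described as finding SAEs that nobody entered.

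A reader might infer more than the text supports:

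- *That only related incidents may enter REDCap.* 8.2 sets a trigger and forbids no other entry, and 8.4 puts all deaths in the eCRF.
- *That control-arm events are certain to be lost from the safety summary or hidden from the DMEC.* The Log should hold all events before any causality judgement, 8.3 does not confine DMEC reports to REDCap data, and 9.2 names no source for the summary. Naming that source is ordinary SAP content, so its absence here is no fault.
- *That detection is so unequal that the arms cannot be described side by side.* ET workers do add contact in the intervention arm, but participants with lower-level needs there are signposted instead of receiving care coordination. In both arms the researcher collects care plans and staff notes at Day 42 and Day 90.

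It is also fair that this is a feasibility trial of 76, with no between-group testing and an intervention described as extremely low risk. That limits the consequence, but an SAE instruction should be unambiguous in any trial.

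**Conclusion.** The contradiction is real and should be corrected before recruitment. Following 8.2 as written leaves unrelated and control-arm SAEs other than deaths with no stated entry step and no deadline, while 8.3 requires every SAE to be reported. The AE definition does not fit the 38 planned controls (half of 76), nor any participant between consent and randomisation.

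The effect on the data is a risk and not a stated outcome. It arises if staff follow 8.2 literally and the descriptive summary is taken from REDCap alone. The number of events involved cannot be given, because the protocol contains no event rates. The events should still be in the Safeguarding Log.

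**What to change.** Reconcile 8.1 to 8.4 in one edit:

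- In 8.2, require every SAE and every death, in either arm and whatever the judged causality, to be entered in REDCap within the existing 24-hour limit from awareness. Record causality as a field on the form, so that it no longer decides entry.
- Let 8.3 and 8.4 refer to that single rule.
- In 8.1, reword the AE definition to cover untoward events in both arms from consent to the final study visit.
- Replace SR with the defined term intended.

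Optional tidying: use the same causality wording for AR and SAR, make the object of the judgement (study or intervention) consistent between 8.1 and 8.2, and list separately any events known only through ET workers. Section 6.4 says the PIs manage safety reporting while 8.2 and 8.3 give the task to the CIs; the same edit can settle that.

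The cost is protocol wording, one eCRF field and a few more entries by existing staff.

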8.3 Responsibilities

ET workers and researchers:

- Record AEs, SAEs, and safeguarding concerns in the Safeguarding Log
- Notify the CIs that a new concern or incident has been added to the Log

CI or their delegate:

- Maintain the Safeguarding Log
- Review concerns or incidents added to the Safeguarding Log
- Ensure concerns or incidents are added to participants' notes on SystemOne as required
- Use experience and judgement to assign causality and determine actions required
- Ensure that all SAEs are recorded and reported to PenCTU and the Sponsor
- Ensure that actions decided on are taken
- Report safety information to the DMEC and TSC

DMEC and TSC:

- Conduct periodic reviews of safety information
- Liaise with one another regarding safety issues

8.4 Notification of deaths

All deaths should be reported to PenCTU within the electronic CRF (eCRF). 'Death' is not an SAE, but the outcome of an SAE, and should be reported in line with Section 8.2.

9. STATISTICS AND DATA ANALYSIS

9.1 Sample Size Calculation

WP1:

The estimated sample size for the workshops for developing the manual for ET workers is N=12, whilst that for the workshops for developing the audio, blog, and film content is N=8. These group sizes will allow for effective communication, diverse perspectives, and meaningful participation.

WP2:

For the feasibility RCT, the target sample size target is N=76 (N=38 per arm). This has been derived from use of a traffic light system to determine whether an RCT is feasible. It is based on the feasibility objectives in relation to the RAG criteria that tests against being in the RED zone (unacceptable outcome) based on an expectation of being in the GREEN zone (acceptable outcome), along with the sample size to give high power to reject being in the RED zone if the GREEN zone holds true (3). The three key feasibility objectives are to assess: (i) recruitment uptake (percent of screened patients recruited), (ii) treatment fidelity, and (iii) participant retention (follow up):

i. Based on the recruitment rate, if we assume the upper boundary of the RED zone is 40% and the lower boundary of the GREEN zone is 60% (designating unacceptable and

- acceptable recruitment respectively), the sample size required for analysis given 80% power and one-sided 5% alpha would be at least N=42 (total screened participants).
- ii. Based on treatment fidelity (defined as having completed the ET assessment and having a written management plan or having been given written resources), if we assume the upper boundary of the RED zone is 60% and the lower boundary of the GREEN zone is 80%, the sample size required for analysis given 80% power and one-sided 5% alpha would be at least N=38 (intervention only).
- iii. Based on follow-up at 90 days, if we assume the upper boundary of the RED zone is 60% and the lower boundary of the GREEN zone is 80%, the sample size required for analysis given 80% power and one-sided 5% alpha would be at least N=38 (total randomised).

The sample sizes across criteria (i)-(iii) are at different levels; (i) is at the level of screened patients, whereas (ii)-(iii) are at the level of recruited patients. To meet criteria (i) we need ns \geq 42 (although we will screen approx. ns \geq 190 (i.e. (1/0.40) × nr (76)) where 0.40 is the expected proportion uptake of the total number screened), and for (ii)-(iii), we need nr = 76 (38 per arm) based on (ii)).

For the embedded formative process evaluation, the estimated sample size is N=48; this includes prisoners from the control and intervention arms (N=20), as well as the ET workers (N=2) and their supervisors (N=2), and other healthcare, prison, and local authority staff (N=24). In the applied scientific realist approach, there is no optimum sample size or saturation point reached through interviews, and it might be more informative to interview a knowledgeable participant multiple times rather than trying to ascertain the experiences of all. As such, final and proposed sample sizes might differ depending on the knowledgeableness of participants.

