2.2 Outcome Measures

Primary Outcomes

WP1:

- A training and supervision manual (nine months after project commencement)
- A fidelity of implementation tool; this will be completed by a researcher in WP2 at the end
 of the three-month intervention to assess whether the intervention has been delivered in
 accordance with the protocol and manual, and to evaluate the quality of delivery
- Audio, blog, event, film, webpage content (18 months after project commencement)

WP2:

For the feasibility RCT, the below traffic light criteria will be used in the decision-making process. However, outcomes will be reviewed as a whole, such that amber or red ratings on one or more of the objectives will not necessarily prevent progression to a full trial:

- Delivery of ET at each site (at end of feasibility RCT)
 - o Green: both sites able to deliver ET
 - o Amber: one site able to deliver ET
 - o Red: no sites able to deliver ET
- Number screened, eligible, and recruited into trial (once marked eligible from screening)
 - o Green: 60% of participants recruited
 - Amber: 40-60% of participants recruited
 - o Red: <40% of participants recruited
- Outcome measure completion rates (at 42- and 90-days ±7 days post-randomisation)
 - o Green: 80% of participants have completeness of >60%
 - o Amber: 60-80% of participants have completeness of >60%
 - o Red: <60% of participants have completeness of >60%
- Intervention adherence and fidelity (at end of feasibility RCT)
 - o Green, amber, and red ratings will be based on the bespoke fidelity tool; as such, the progression criteria will be developed once the tool has been finalised.
- Retention rates (at 90-days ±7 days post-randomisation)
 - o Green: 60% of participants
 - o Amber: 40-60% of participants

- o Red: <40% of participants
- Proportion transferred and/or released during follow-up (at 42- and 90-days ±7 days postrandomisation)

Outcome measures for the cost-effectiveness feasibility analysis will include:

- Completeness of care plans, case notes, and resource use questionnaires
- Potential cost of ET (based on data from the Personal Social Services Resource Unit)
- Assessment of the feasibility of conducting a Budget Impact Analysis (BIA)
- List of suitable variables for a social Return On Investment (ROI) analysis

Outcome measures for the realist-informed process evaluation will include:

• Refined IPT, logic model, and intervention delivery platform.

Secondary Outcomes

WP2:

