6.9 End of Trial

The end of the feasibility RCT is defined as the completion of the final participant's final outcome measures. The end of the study is defined as the conclusion of the final participant's last interview or visit. At this point, the research team will submit a checkpoint report based on the progression criteria. If the minimum success criteria for key feasibility aims and objectives are achieved, the programme will progress to a full RCT. The sponsor delegate will notify the REC of the end of the trial within 90 days of completion. The final report will be written within 12 months of the end of the trial. If the trial terminates early for any reason, the CI will notify the REC of early termination (including reasons for this) or end of trial in accordance with the required timelines.

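### N=76 is justified by one-sided 5%, 80% power tests against RED, but the traffic-light rule and analysis as written do not carry those error rates

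*Protocol*

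**What the plan says.** **Sizing (Protocol 9.1).** The sample size is built on the RAG criteria as a test against RED, with "the sample size to give high power to reject being in the RED zone if the GREEN zone holds true". Three objectives are sized:

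- Recruitment, RED limit 40%, GREEN limit 60%: "the sample size required for analysis given 80% power and one-sided 5% alpha would be at least N=42 (total screened participants").
- Fidelity, 60% and 80%: "the sample size required for analysis given 80% power and one-sided 5% alpha would be at least N=38 (intervention only").
- Retention at 90 days, 60% and 80%: "the sample size required for analysis given 80% power and one-sided 5% alpha would be at least N=38 (total randomised").

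Fidelity, at 38 in the intervention arm, sets the total of 76. Section 9.1 plans to screen about 190, from an expected uptake of 0.40.

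**Decision rule (Protocol 2.2).** Observed percentages are placed in bands. Recruitment and retention both have RED below 40%, AMBER 40 to 60% and GREEN at 60%. Fidelity bands are deferred until the fidelity tool is finished. Recruitment is counted among those found eligible at screening, whereas 9.1 counts among those screened. Results are reviewed as a whole, and "amber or red ratings on one or more of the objectives will not necessarily prevent progression to a full trial".

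**Analysis (Protocol 9.2).** "Descriptive statistics will be reported for feasibility outcomes". No test, confidence limit or critical count against the RED limit is given.

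**Consequence (Protocol 6.9, repeated in substance in 13.1).** "If the minimum success criteria for key feasibility aims and objectives are achieved, the programme will progress to a full RCT".

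**The concern.** A sample size at 5% alpha and 80% power describes a particular procedure: reject RED only when the observed count reaches a critical value. That value lies well above the RED limit itself. Section 2.2 moves a result out of RED as soon as the observed percentage reaches the limit, which is a different and more lenient procedure. A reader of 9.1 would believe that a truly unacceptable rate has at most a 5% chance of leaving RED, and the rule in 2.2 does not provide that protection. The traffic-light result feeds the checkpoint report on whether to run a full RCT, so those who use it should know what a rating of not RED does and does not establish.

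**Working it through.** **1. Reproduce the plan's own figures.** One-sample proportion, one-sided 5%, 80% power, with continuity correction:

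n0 = [(1.645·√(p0q0) + 0.842·√(p1q1)) / (p1 − p0)]²; n = (n0/4)·[1 + √(1 + 2/(n0·(p1 − p0)))]²

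- p0 = 0.40, p1 = 0.60: n0 = 37.1, n = 41.95, so 42.
- p0 = 0.60, p1 = 0.80: n0 = 32.6, n = 37.46, so 38.

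Both match 9.1. Without the correction the results are 38 and 33, which do not match. The sizing therefore assumes a formal test. Its exact critical counts are 23/42 (54.8%; alpha 3.8%, power 80.3%) and 29/38 (76.3%; alpha 2.7%, power 78.4%).

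**2. Error rates of a rule that bands the observed percentage.** X is binomial(n, p). Not RED means X/n is at or above the RED limit; GREEN means X/n is at or above the GREEN limit. Limits are those of 9.1.

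| Objective | n | Limits | Not RED, true rate at RED limit | GREEN, true rate at RED limit | GREEN, true rate at GREEN limit |
|---|---|---|---|---|---|
| Recruitment | 42 | 40/60 | P(X≥17) = 53.3% | P(X≥26) = 0.34% | 46.7% |
| Recruitment | 190 | 40/60 | P(X≥76) = 52.8% | <0.01% | 53.1% |
| Fidelity | 38 | 60/80 | P(X≥23) = 54.4% | P(X≥31) = 0.40% | 50.0% |
| Retention | 76 | 60/80 | P(X≥46) = 51.2% | P(X≥61) = 0.01% | 54.6% |

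The sixth column is the power if GREEN is taken as the pass: 47 to 55%, against the stated 80%.

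**3. Retention under the bands in 2.2 (40/60), n = 76.**

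- True rate 40%, the RED limit in 2.2: P(X≥31) = 48.8% not RED.
- True rate 60%, the RED limit in 9.1: P(X≥31) = 99.98% not RED, and P(X≥46) = 51.2% GREEN.

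A retention rate that 9.1 treats as unacceptable almost never rates RED under 2.2, and rates GREEN about half the time.

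**4. Smallest counts that rule out RED at one-sided 5% (exact).**

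| Objective | Count | Alpha | Power at GREEN limit |
|---|---|---|---|
| Fidelity, 60/80 | 29/38 (76.3%) | 2.7% | 78.4% |
| Retention, 60/80 | 54/76 (71.1%) | 3.0% | 97.8% |
| Retention, 40/60 | 38/76 (50.0%) | 4.9% | 97.0% |
| Recruitment, 40/60, n = 190 | 88/190 (46.3%) | 4.5% | >99.9% |

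All four counts fall inside AMBER. AMBER therefore mixes results that exclude RED with results that do not.

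**The case against.** **AMBER is not a pass.** A reader might infer a false-pass rate of about 50%. The documents do not support that. Not RED is not the same as a pass, nearly all of the 50% is AMBER, and a false GREEN at the 9.1 RED limits is at most 0.4%. Section 2.2 also makes the review holistic, so the protocol fixes no single error rate for progression. This stands, and it limits the claim to the classification. It does not rescue 9.1, whose alpha refers to rejecting RED.

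**Some figures rest on limits that 2.2 does not set.** Section 2.2 has no fidelity bands, gives retention 40/60 rather than 60/80, and counts recruitment among the eligible. This stands. The fidelity figure is an assumption from 9.1, and the retention figure depends on which section prevails. The 190 is only 76/0.40, and 2.2's denominator would give a different n.

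**Requiring RED to be ruled out would be harsh.** A reader might want it mandatory on all three objectives. Section 9.1 expects 40% uptake, exactly its RED limit, so the recruitment test at n = 190 would succeed only about 4.5% of the time. This stands against a mandatory gate.

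**The test may sit in a separate SAP.** Section 9.2 excludes only between-group comparisons, so an interval or one-sample test is not forbidden, and a SAP could supply one. That would help, but the mismatch is between what 9.1 claims and what 2.2 and 9.2 of the same protocol state. It should be settled there.

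**Conclusion.** The concern holds as a mismatch between the sizing and the stated rule. Sections 2.2 and 9.2 do not deliver the 5% alpha and 80% power by which 9.1 justifies N=76. At the 9.1 RED limits the chance of not being classed RED is 51 to 54%, mostly AMBER. If GREEN is the pass, power at the GREEN limit is 47 to 55%. For retention the two sections also disagree on the limits, and with 2.2's bands a true 60% leaves RED 99.98% of the time.

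The figures assume independent participants, final counts of 38, 76 and 42 or 190, and a result exactly on a limit taking the better rating. The fidelity figure also assumes the 60/80 limits of 9.1. The sample sizes themselves are computed correctly, and the arithmetic alone does not show N=76 to be too small.

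**What to change.** 1. Reconcile the retention limits (40/60 in 2.2, 60/80 in 9.1) and the recruitment denominator (eligible in 2.2, screened in 9.1).
2. In 2.2 and 9.2, report each key proportion with its exact one-sided 95% lower limit and state whether that limit exceeds the RED limit. The matching counts are at least 29/38 for fidelity if 60/80 is adopted; at least 54/76 for retention at 60/80 or 38/76 at 40/60; and the corresponding count for the final recruitment denominator. Recompute them if the numbers analysed differ.
3. Split AMBER into RED ruled out and RED not ruled out.
4. Keep this as an input to the holistic review, not a mandatory gate on all three objectives.

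Otherwise, delete the alpha and power claim from 9.1 and justify N=76 by confidence-interval precision. For example, at an observed 80% the approximate 95% half-width is 1.96·√(0.8·0.2/38) = 12.7 percentage points for fidelity and 1.96·√(0.8·0.2/76) = 9.0 points for retention.

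The cost is a few sentences, three extra intervals and a slightly stricter reported rating. No extra participants are needed.

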6.6 Participant Retention

Attrition will be minimised by asking for transfer holds for all participants for the duration of their time in the feasibility RCT (with their consent) and requesting community contact details and/or permission to contact them through the National Probation Service. If prisoners are transferred, we will attempt to follow them up in other prisons in the estate. If prisoners are released into the community, we will offer them options for completing the study measures through digital means, face-to-face or telephone interviews, or on paper. We will also measure numbers of participants who exit the study through release or transfer, as this will inform the feasibility of a full RCT.

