6.8 Withdrawal Criteria

For WP1 and WP2, the PIS will explain that participants are able to decline or withdraw from the study if they wish to, without giving a reason and without prejudice to future care. The reasons for deciding to withdraw are varied; participants may, for example, find that they are no longer willing to engage in the research, or have other programmes that they would prefer to prioritise. Their

reasons for discontinuation will be requested and recorded in REDCap in a withdrawal form, but their right not to state a reason will be respected. Data collected from the participant prior to their withdrawal will remain on REDCap. The characteristics of the participants who withdraw or are lost to follow-up will be compared with those that remain within the trial.

For the feasibility RCT, participants might also withdraw from the study due to being transferred or released. However, attempts will be made to minimise attrition (Section 6.6). In addition, early discontinuation will be allowed, and participants that withdraw their consent for the treatment element of the feasibility RCT can still be invited to complete the outcome measures. In addition, participants who withdraw their consent for the feasibility RCT element of WP2 can still be invited to take part in the process evaluation element of WP2.

For WP2, for participants lacking capacity to consent, if there is any indication that they do not want to take part, the researchers will prioritise their interests and withdraw them from the study. No participants lacking capacity to consent will be recruited for WP1.

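### The 90-day retention sample size in Section 9.1 uses 60/80 boundaries, but the governing progression criterion in Section 2.2 uses 40/60

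*Protocol*

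**What the plan says.** Section 2.2 (Outcome Measures) lists the progression criterion as "Retention rates (at 90-days ±7 days post-randomisation"), with three bands: "Green: 60% of participants", "Amber: 40-60% of participants" and "Red: <40% of participants". A footnote to the outcome list in the trial summary refers to Section 2.2 for the traffic-light criteria. Section 2.2 adds that outcomes are judged together, so an amber or red rating on one of them need not stop progression.

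Section 9.1 (Sample Size Calculation) says the target of 76 was derived from the traffic-light criteria, as a test against the Red zone with high power if the Green zone is true. Red stands for an unacceptable outcome and Green for an acceptable one. Its third key objective is ("iii) participant retention (follow up"). The calculation for it begins: "Based on follow-up at 90 days, if we assume the upper boundary of the RED zone is 60"%. It puts the lower Green boundary at 80% and arrives at 38 randomised participants, with 80% power and one-sided 5% alpha.

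**The concern.** Both sections concern the same outcome at the same visit, and Section 9.1 says it takes its boundaries from the traffic-light criteria. For recruitment the boundaries do agree, at 40% and 60% in both places. For retention they do not: the top of the Red zone is 40% in one section and 60% in the other, and the bottom of the Green zone is 60% in one and 80% in the other. The protocol gives no reason for the difference.

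Retention is one of the three objectives that Section 9.1 uses to justify the sample size, and it feeds the checkpoint report on progression to the full trial. As written, a result that the sample-size section places in its unacceptable zone can be reported as Amber, and a result short of its acceptable boundary can be reported as Green. If the mismatch is noticed only at the end, the scale would have to be settled with the retention figure already known.

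**Working it through.** **Inputs.** Section 2.2 retention boundaries: 40% and 60%. Section 9.1 (iii) boundaries: p0 = 60% (top of Red) and p1 = 80% (bottom of Green). Section 9.1 also gives one-sided alpha 5%, power 80%, a stated N of 38 for (iii), a stated N of 42 for recruitment (40/60), and a target of 76 randomised.

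**Step 1: reproduce the stated figure.** One-sample test of a proportion, normal approximation:

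n = [(1.645·√(p0(1−p0)) + 0.842·√(p1(1−p1))) / (p1−p0)]²

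with continuity correction n_c = (n/4)·[1 + √(1 + 2/(n·(p1−p0)))]².

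- 60/80: n = [(1.645·0.490 + 0.842·0.400)/0.20]² = 32.6; n_c = 37.46, so **38**, as stated for (iii).
- 40/60: n = [(1.645·0.490 + 0.842·0.490)/0.20]² = 37.1; n_c = 41.95, so **42**, as stated for recruitment.

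The corrected formula reproduces both figures, so it is taken as the method used. By that method the Section 2.2 retention boundaries require 42, not 38. Without the correction, 40/60 would also round up to 38. That is a coincidence: the uncorrected formula would not give the stated 42 for recruitment, and Section 9.1 (iii) names 60% and 80% explicitly.

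**Step 2: check the target.** Both 38 and 42 are below 76, which is set by criterion (ii), 38 in the intervention arm. Exact binomial at n = 76:

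- 60/80: reject Red at 54 or more retained; alpha 0.030, power 0.978.
- 40/60: reject Red at 38 or more retained; alpha 0.049, power 0.970.

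**Step 3: convert the boundaries to counts out of 76.** 40% is 30.4, 60% is 45.6 and 80% is 60.8. No count falls exactly on a boundary.

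| Retained of 76 | Section 2.2 | Section 9.1 (iii) |
|---|---|---|
| 30 or fewer (up to 39.5%) | Red | Red zone |
| 31-45 (40.8%-59.2%) | Amber | Red zone |
| 46-60 (60.5%-78.9%) | Green | above Red, below the Green boundary |
| 61 or more (80.3% and up) | Green | Green zone |

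**Step 4: how often the difference would show.** The documents give no expected retention beyond these boundaries, so the true rates below are assumptions. Exact binomial, n = 76:

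| Assumed true retention | Green under 2.2 | At or above the Green boundary of 9.1 | Count falls in 31-60, where the sections differ |
|---|---|---|---|
| 50% | 0.042 | 0.000 | 0.958 |
| 60% | 0.512 | 0.000 | 1.000 |
| 65% | 0.826 | 0.003 | 0.997 |
| 70% | 0.971 | 0.030 | 0.970 |
| 75% | 0.998 | 0.178 | 0.822 |
| 80% | 1.000 | 0.546 | 0.454 |

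**The case against.** The strongest reply is that there is no doubt about which scale produces the rating. Section 2.2 says its criteria are the ones used for the decision, and the trial summary refers to it. Section 9.1 works from assumed values to justify a number, and that number does not change. Ratings are also weighed together. All of this stands, and it limits the point to a sample-size basis that does not match the criterion it claims to rest on. It does not remove the mismatch: Section 9.1 says its boundaries come from the traffic-light criteria, and for retention they do not. Joint review settles how a rating is weighed, not where its boundaries lie. Sections 6.9 and 13.1 also tie progression to minimum success criteria.

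A reader might infer more, and three such readings are not supported:

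- **Transfer and release.** Section 6.8 says "participants might also withdraw from the study due to being transferred or released", while Section 6.6 says "If prisoners are transferred, we will attempt to follow them up in other prisons in the estate". This may look like a contradiction about who counts as retained. But Section 6.8 goes on to refer to Section 6.6 for limiting attrition. Read together, follow-up is attempted and some people are still lost.
- **Completion.** Green for outcome completion needs 80% of participants and Green for retention needs 60%, which might seem incompatible. That follows only if both are counted over everyone randomised, and Section 2.2 does not state the completion denominator.
- **A middle band in Section 9.1.** That section describes only its Red and Green zones. It does not label results between 60% and 80%, so the table in the working says only that they lie between the two boundaries.

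**Conclusion.** The inconsistency is real and needs correcting: the retention threshold in Section 2.2 or the retention sample-size basis in Section 9.1 is wrong as written. It affects every result from 31 to 60 retained of 76. Below 40% and from 80% upward the sections agree. The size of N for (iii) is 38 or 42 depending on the scale, and 76 covers both with power of about 0.97 or more.

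These figures assume that all 76 are randomised and form the denominator, that Section 9.1 used the continuity-corrected one-sample formula, and that participants' outcomes are independent.

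A reader might conclude that the trial has two competing rating scales and no way to choose between them, or that 60/80 must be the intended one. The documents support neither. Section 2.2 governs the rating, and nothing shows which scale was meant.

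**What to change.** Before any data are seen, use one retention scale in both sections. Either option resolves the mismatch:

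1. **Change Section 2.2 to the scale Section 9.1 was powered on:** Green at 80% or more, Amber from 60% to below 80%, Red below 60%. N=38 for (iii) stands. The criterion becomes harder to pass: with 76 randomised and true retention of exactly 80%, the chance of an observed Green is about 0.55.
2. **Keep 40/60 in Section 2.2** and restate Section 9.1 (iii) with a Red upper boundary of 40%, a Green lower boundary of 60% and N=42.

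In the same edit, state that retention is counted over all randomised participants, including those transferred or released. Separate reporting of transfers and releases is already planned in Sections 2.2, 2.3 and 6.6, so nothing need be added there.

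The cost is protocol wording. The target of 76 does not change under either option.
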